#### **Research Abstract**

#### Please type your Research Abstract here:

The Research Abstract should summarize the main points of your study in one paragraph. The following guidelines may help you:

- 1. Purpose and objective (1-2 sentences)
- 2. Study activities and population group (2-4 sentences)
- 3. Data analysis and risk/safety issues (1-2 sentences)

Tobacco smoking and chronic pain are highly comorbid conditions. Nicotine has been shown to provide mild, short-term anti-nociceptive effects, which may contribute to powerful negative reinforcement learning. Conversely, smoking withdrawal exacerbates pain, presenting a potential barrier to smoking cessation. The goal of the proposed research is to examine whether switching to Very Low Nicotine Content (VLNC) cigarettes can directly weaken the pain-smoking reinforcement cycle, and attenuate withdrawal-induced hyperalgesia, among smokers with chronic pain, in order to better understand the mechanisms underlying smoking-pain comorbidity. Adult, non-treatment seeking daily smokers with chronic (> 3 months) non-cancer back pain will complete 1-week of baseline ecological momentary assessment (EMA) while smoking their usual brand of cigarettes to familiarize them with study procedures; they will then be randomized to 4-weeks of Normal Nicotine Content (NNC) or VLNC cigarettes. EMA will continue during weeks 1 and 4 of study cigarette use, and will assess smoking behavior and urge, negative affect, and pain intensity and interference. Participants will attend weekly in-person visits to obtain biomarker verification of cigarette compliance, and will complete measures of nicotine dependence, selfefficacy and motivation to quit, and pain-related coping. At the start of the study and at the end of 4weeks of study cigarette use, a 24-hr smoking abstinence test will be used to assess withdrawal symptoms and withdrawal-induced hyperalgesia. Participants will also be contacted by telephone 3 months after study participation to assess quitting behaviors, including actual quit attempts and use of cessation strategies. Analyses will examine the effects of NNCs versus VLNCs on pain and smoking-related measures assessed during EMA, weekly visits, and pre- and post-intervention abstinence tests. Risks of the study include withdrawal symptoms during the 24-hr abstinence sessions and during initial use of VLNCs, risks associated with smoking investigational cigarettes, and risks associated with the collection of personal information.

# Research Summary

#### State your primary study objectives

- 1. To examine the effects of NNCs versus VLNCs on smoking and pain over 4 weeks of study cigarette use and following a 24-hour abstinence challenge.
- 2. To examine the effects of NNCs versus VLNCs on the bidirectional, within-person associations between momentary reports (as assessed with EMA) of smoking urge/behavior, pain, and negative affect.

# **State your secondary study objectives**

1. To examine the effects of NNCs versus VLNCs on changes in smoking and pain-related cognitions, including interest in guitting smoking, abstinence self-efficacy, and smoking to cope with pain.

#### Please select your research summary form:

Standard Research Summary Template

This is the regular (generic) research summary template which is required for all regular applications (unless your protocol fits under the other research summary templates in this category). Use of these instructions is helpful for ensuring that the research summary contains all necessary elements.

### **Standard Research Summary**

### **Purpose of the Study**

Objectives & hypotheses to be tested

The purpose of the study is to evaluate the effects of switching to VLNC cigarettes as a potential strategy for disrupting the pain-smoking reinforcement and withdrawal cycle among smokers with chronic back pain. Adult daily smokers with chronic (> 3 months) non-cancer back pain will be randomly assigned to 4-weeks of Normal Nicotine Content (NNC) or VLNC investigational cigarette use. Participants will attend weekly assessment visits during this time, and will complete EMA assessments during a baseline week of usual brand smoking, and during weeks 1 and 4 of study cigarette use. Participants will also complete assessments of pain and withdrawal following 24 hours abstinence at the start of the study and after 4 weeks of study cigarette use.

Aim 1 will examine effects of NNCs versus VLNCs on smoking and pain over the 4 weeks of study cigarette use and during the 24-hour abstinence tests.

Hypothesis 1a: VLNCs will lead to reductions in nicotine dependence and frequency of smoking over the course of study cigarette use, whereas no change will be observed for NNCs.

*Hypothesis 1b:* Relative to the pre-intervention baseline, smokers assigned to VLNCs will report decreased pain intensity and interference and fewer withdrawal symptoms during the post-treatment 24-hr abstinence test compared with smokers in the NNC condition.

Aim 2 will examine effects of NNCs versus VLNCs on the bidirectional, within-person associations between momentary reports (as assessed with EMA) of smoking urge/behavior, pain and negative affect.

Hypothesis 2a: VLNCs will reduce the magnitude of the within-person associations between momentary reports of pain/negative affect and smoking urge/intent to smoke.

Hypothesis 2b: VLNCs will reduce the magnitude of the within-person association between recent smoking and reports of decreased pain and negative affect.

**Exploratory Aim 3** will examine the effects of NNCs versus VLNCs on changes in smoking and pain-related cognitions, including interest in quitting smoking, abstinence self-efficacy, and smoking to cope with pain.

*Hypothesis:* Following VLNCs, participants will report increased motivation and intention to quit smoking, greater abstinence self-efficacy, and decreased use of smoking as a pain-related coping strategy.

# **Background & Significance**

Should support the scientific aims of the research

Tobacco smoking and chronic pain are highly comorbid conditions, and carry a combined annual price tag of more than \$900 billion in health-care costs and lost productivity. Epidemiological studies demonstrate that smoking rates among individuals seeking treatment for chronic pain are at least twice those of the general population. Moreover, regular tobacco use is an independent risk factor for development of chronic pain conditions. Smoking and pain have been proposed to influence each other through a reciprocal positive feedback loop, in which pain increases motivation to smoke, and smoking worsens pain over time. Laboratory studies suggest that nicotine has mild anti-nociceptive effects, which are likely to contribute to powerful negative reinforcement of smoking behavior with repeated use. At the same time, initial smoking abstinence (12-24 hrs) is associated with *increased* pain that is correlated with craving and severity of withdrawal, presenting a significant barrier to cessation. Together, the combination of nicotine's analgesic effects and increased pain during withdrawal are likely to perpetuate smoking, contributing to worsening pain, while decreasing expectations that smoking cessation is possible. **Once this cycle is instantiated in habitual behavior, there are no known strategies for disrupting it, and effective smoking cessation interventions are extremely limited.** 

The primary objective of this project is to experimentally evaluate the effects of switching to 4 weeks of very low nicotine content (VLNC) cigarettes on the pain-smoking reinforcement and withdrawal cycle among non-treatment seeking smokers with chronic back pain. Our previous work demonstrated that VLNCs decrease nicotine dependence and withdrawal in both treatment-seeking and non-treatment seeking populations, representing a powerful tool for decoupling the reinforcing effects of nicotine from the behavior of smoking. Importantly, VLNCs are effective at reducing craving by maintaining the sensorimotor and behavioral aspects of smoking, whereas the minimal level of nicotine delivery facilitates extinction of

smoking behavior leading to decreased dependence with repeated use. Although VLNCs carry the same health risks as normal nicotine content (NNC) cigarettes, evidence indicates that switching to VLNCs increases interest in quitting, promotes abstinence self-efficacy, and improves cessation, suggesting that VLNCs may be a useful intermediate step for smokers unable to quit.

Despite the utility of VLNCs as a smoking cessation aid in the general population, the effect of VLNCs on real-world pain and smoking behavior among individuals with chronic pain has not been investigated. Laboratory studies of acute pain manipulations suggest that VLNCs provide intermediate pain relief relative to NNCs or no smoking, suggesting that VLNCs may help to attenuate withdrawal-induced hyperalgesia among smokers with chronic pain. However, there is tremendous need to extend mechanistic findings from laboratory studies to examine the complex interactions between pain perception and real-world smoking behavior among individuals with chronic pain. VLNCs provide an opportunity to directly examine the relative contribution of nicotine and non-nicotine factors to the association between smoking and pain in the real world, representing a critical first step to developing targeted interventions that can reduce smoking and improve pain outcomes in this population.

The proposed project will apply well-validated, rigorous and reproducible methods, including ecological momentary assessment (EMA), randomization to VLNC or normal nicotine content (NNC) cigarettes, and stringent biochemical verification of adherence, to examine proximal clinically-relevant outcomes as a precursor to further intervention development. This research will disentangle the relative contribution of nicotine and non-nicotine factors to smoking/pain comorbidity—information critical to advancing our understanding of the mechanisms driving smoking/pain comorbidity, and will pave the way for a large-scale randomized clinical trial incorporating VLNCs to promote smoking cessation in the context of chronic pain.

#### **Design & Procedures**

Describe the study, providing details regarding the study intervention (drug, device, physical procedures, manipulation of the subject or the subject's environment, etc.). Discuss justifications for placebo control, discontinuation or delay of standard therapies, and washout periods if applicable. Identify procedures, tests and interventions performed exclusively for research purposes or more frequently than standard of care. Include alternative therapies, concurrent therapies discontinued per protocol, risk benefit ratio, and use of tissue/specimens. Discuss monitoring during washout periods if applicable. Include brief description of follow-up, if any.

**Overview of Study Design.** Participants will complete an initial screening session in which informed consent will be obtained, eligibility is confirmed, and baseline pain and smoking measures are collected. Eligible participants will then be scheduled for a training session/initial abstinence test session. Participants will be asked to abstain from smoking for 24 hours prior to this session. They will complete survey measures, and then will receive training on the EMA procedures and the Metric Wire software will be installed on their smartphone device. Participants will then complete a 1-week baseline period of EMA while smoking their usual brand of cigarettes. Following the baseline period, participants will return for an in-person visit and will be randomly assigned to smoke VLNCs (n=24) or NNCs (n=24) for the next four weeks. Participants will complete 4 weekly lab visits, during which study cigarettes will be supplied and study measures collected. In addition, EMA will continue to be conducted during weeks 1 and 4 of study cigarette use. At the end of study cigarette use, participants will complete a second abstinence challenge session to assess pain and withdrawal following 24 hrs abstinence from smoking. Finally, participants will be contacted by telephone 3 months after completing the study to provide information about quitting behaviors. Details of study sessions are described below and are presented in Table 1.

Screening Session (up to 3 hours). Participants will first complete a phone screening interview, during which the study will be described in detail and preliminary participant characteristics (e.g., age, smoking and pain status and number of cigarettes smoked per day) will be assessed. Those participants who meet preliminary criteria for participation will be scheduled for a comprehensive screening session. During this session all aspects of the study will be described, a photo ID will be documented to confirm age and identify, and informed consent will be obtained. Breath and urine samples will be collected to confirm a) negative urine drug screen (other than marijuana); b) breath alcohol level (BAL) equal to 0.000 (required at all visits); c) breath CO > 10 ppm; and d) negative pregnancy test for females who are capable of becoming pregnant. Use of illegal drugs will be exclusionary. Marijuana use will not be exclusionary, but participants must agree to not use marijuana for 48 hours prior to sessions and must avoid any additional tobacco such as cigarillos. In addition, daily marijuana users will be excluded. Tobacco use history and medical history will be obtained, and vital signs (heart rate, blood pressure) will be measured. A psychiatric screening will be conducted using the M.I.N.I. Pain and smoking-related self-report measures will be administered via Redcap. Pain intensity and interference inclusion criteria will be assessed with the Graded Chronic Pain Scale (GCPS). History of chronic back pain will be confirmed through the participant's medical record or by provider. If the participant is a non-Duke patient or is a Duke patient not recruited using Duke MyChart, a release form will be signed. If participants are recruited using Duke MyChart, a release form will be signed. If participants are recruited using Duke MyChart, be release form will be signed. If participants are recruited using Duke MyChart, a release form will be signed. In person screening component. All screening materials will be review

Baseline Abstinence/Training Session. Following screening, participants will complete a baseline abstinence challenge session, in which they are asked to abstain from smoking for 24 hours prior to the session. Expired CO < 6 ppm or 50% reduction from baseline will be used to verify abstinence. Participants will complete measures of craving, pain, and withdrawal. At the conclusion of the session, Metric Wire software will be installed on their smartphone, and they will be trained in the procedures for EMA.

Weekly Sessions. After one week of baseline EMA while smoking of usual brand cigarettes, participants attend an in-person visit (V1), during which they will be randomized to NNC or VLNC condition, given a supply of study cigarettes, and provided with a schedule of 4 weekly follow-up visits (V2 through V5). During each of the weekly visits participants will complete self-report measures and a timeline follow-back of past-week smoking, other tobacco use and alcohol/substance use; additional study cigarettes will be supplied; and breath CO and urinary measures of nicotine exposure will be collected. Adverse events will be monitored, as well as changes in medical history including new or discontinued medications, new treatments for current medical problems, or other study participation.

Post-Intervention Abstinence Session. Immediately following the final weekly visit, participants will be asked to abstain from smoking for 24 hours prior to attending a final laboratory abstinence session. Procedures and measures will be identical to those used in the initial abstinence session.

Follow-Up 3-Month Phone Call. Participants will be contacted by phone 3 months after completing the study to provide information about current smoking, recent quit attempts, and cessation strategies used.

Table 1. Schedule of Events and Procedures

CIGARETTES		UB	NNC	NNC or VLNC Cigarettes							
REMOTE ASSESSMENT		EMA			E			EMA			
IN-PERSON VISITS	Screening	24hr / Test 1 Traini (A1)	./ ng	Visit Week 1 (V1)	Visit Week 2 (V2)	Visit Week 3 (V3)	Visit Week 4 (V4)	Visi We 5 (V5	ek A	ABS Test 2 A2)	
Study Day	-30 to -1	0		7	14	21	28	35	3	36	
Window (in days)		0		(± 2)	(± 2)	(± 2)	(± 2)	) (±	2) (	± 1)	
PROCEDURES					-						
Informed Consent	Х								Î		
Eligibility	Х										
Demographics	Х										
Medical History	Х										
Tobacco History	Х										
Breath CO Sample	Х	Х		X	Х	Х	Х	Х	>	(	
Breath Alcohol	Х	Х		X	Х	Х	Х	Х	>	(	
Urine Drug Screen	х										

Psych Assessment (MINI)	X										
Cognitive Function (WRAT)	х										
Metric Wire install and EMA training		Х									
STUDY CIGARETTES											
Randomization			Х								
Study Cigarettes Supplied			х	х	Х	х					
Product Accountability				Х	Х	х	Х				
Timeline Follow-back			Х	Х	Х	х	Х				
Urine Sample (TNEs)*				Х	Х	X	Х				
SAFETY ASSESSMENTS											
Medications	х	x	Х	Х	Х	х	Х	X			
Vital Signs	X	X	Х	Х	X	х	Х	X			
Pregnancy Test	х		Х								
Respiratory Health/ Side Effects Forms	X	×	X	×	×	×	×	X			
Adverse Events		x	х	х	X	х	х	Х			
PRIMARY AND SECONDA	RY OUTCOME	MEASURES	5	Į.			l .	Į			
Cigarette Dependence	х		х	х	Х	х	х				
Craving/Withdrawal	Х	X	х	х	Х	х	х	Х			
Pain Intensity/ Interference	x	X	Х	x	×	Х	x	х			
Quit Self-Efficacy	х		х		X		х				
Motivation to Quit	х		х		X		х				
Pain-Related Cognitions	×	×	x		Х		×	Х			

**UB:** Usual brand cigarettes; **NNC:** Normal nicotine content research cigarettes; **VLNC:** Very low nicotine content research cigarettes; **EMA:** Ecological momentary assessment; **CO:** Carbon monoxide; **M.I.N.I.:** Mi ni International Neuropsychiatric Interview; **WRAT:** Wide Range Achievement Test-4 (Word Reading Subtest); **TNEs:** Total Nicotine Equivalents

\*Note that urine samples will be collected at all visits to increase perception that study cigarette adherence may be biochemically verified at any time, but only weekly visits 4 and 5 of the VLNC group will be analyzed for TNEs.

Study Procedures. Details of specific procedures involved in the study are described below.

VLNCs and NNC Cigarettes. SPECTRUM cigarettes will be ordered through NIDA (NOT-DA-14-004) and will have the following nicotine content and yield: NNC cigarette condition. NRC600/601 (non-menthol /menthol) has a nicotine content of approximately 15.8 mg/g tobacco with reported nicotine yield (ISO) of  $0.8 \pm 0.15$  mg and a tar yield of  $10.5 \pm 1.5$ . This NNC dose was chosen because it is similar to full flavor cigarettes and is associated with similar rates of smoking, nicotine levels and dependence as the usual brand cigarettes. VLNC cigarette condition. NRC102/103 (non-menthol/menthol) has a nicotine content of approximately 0.4 mg/g tobacco with reported nicotine yield (ISO) of  $0.03 \pm 0.01$  mg and a tar yield of  $9 \pm 1.5$ . This dose was chosen because prior studies have shown that the VLNC dose relative to NNC showed significant reductions in cigarettes smoked per day, nicotine exposure and cigarette dependence. These cigarettes have been used previously in our lab in several studies (R01 DA042532; R01 DA048454; U54 DA031659).

Study Cigarette Adherence. Compliance data will be examined using methods standardized in our prior research (e.g., comparing daily reports, returned product packaging, and timeline follow-back; providing feedback on inconsistencies). To encourage adherence to study cigarettes, urine samples will be collected at each study visit; participants will be told that 2 will be randomly selected for biomarker analysis to identify non-compliance. As in our prior work,  participants in the VLNC group will receive \$600 bonus payment contingent on biochemical verification of self-reported adherence, defined as total nicotine equivalents at or less than 12 nmol/mL at weekly visits 4 and 5. This cutoff allows for only minimal use of non-study cigarettes, while ensuring adequate sensitivity to detect adherence. To encourage honest reporting, participants disclosing non-study cigarette or other tobacco use will receive a reduced bonus of \$200. We have used this tiered incentive approach in a prior 20-week study and observed biochemical verification indicating 54-69% compliance. Adherence in the proposed research will likely be higher given the shorter duration of use. Biochemical analysis is not available to confirm exclusive use of NNC cigarettes; thus bonuses in the NNC group will be based solely on self-report. Compliance is more likely in the NNC condition given that rates of usual-brand and NNC smoking were nearly identical in our prior study. Effects of compliance will be examined in sensitivity analyses restricted to those with verified VLNC adherence.

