### Exclusion criteria

- actively taking steps to quit smoking;
- inability to attend all required experimental sessions;
- report of significant health problems including but not restricted to untreated chronic hypertension, emphysema, seizure disorder, history of significant heart problems;
- systolic blood pressure > 160 or diastolic blood pressure > 100 (participants failing for blood pressure will be allowed to rescreen once);
- resting heart rate > 100 (participants failing for heart rate will be allowed to rescreen once);
- breath alcohol level > 0.000 (participants failing for BAL will be allowed to rescreen once);
- current use of prescription opioid pain relievers;
- lifetime history of bipolar or psychotic disorder;
- current unstable psychiatric disorder as assessed by the MINI;

- suicidal ideation with plan or intent; potential subjects who endorse items 4 (Active Suicidal
  Ideation with Some Intent to Act, without Specific Plan) and/or 5 (Active Suicidal Ideation with
  Specific Plan and Intent) on the Columbia Suicide Severity Rating Scale will be excluded from study
  participation, and referred to appropriate psychiatric treatment;
- use of non-cigarette tobacco products or electronic cigarettes > 8 times in past 30 days;
- current use of nicotine replacement therapy (NRT) or other smoking cessation strategy;
- use of Spectrum investigational cigarettes or low nicotine content cigarettes in the past year;
- quit attempt in the past 30 days resulting in greater than 3 days abstinence;
- past year alcohol or substance use disorder;
- use of illegal drugs as measured by urine drug screen (other than marijuana);
- daily or near-daily use of cannabis;
- primary pain complaint was due to specific medical conditions (e.g., cancer, rheumatoid arthritis, or complex regional pain syndrome);
- spine surgery within the past year or planned surgery within the timeframe of the study;
- positive pregnancy test among women

Changes to inclusion criteria made to reflect changes in criteria surrounding pain rating, now incorporating worst pain rating.

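### The 24-hour challenges ask only for abstinence from smoking and check it only by breath CO, so e-cigarette nicotine at the post-intervention test would go undetected

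*Combined protocol and SAP*

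**What the plan says.** **Instruction.** The Overview of Study Design says of the baseline session: "Participants will be asked to abstain from smoking for 24 hours prior to this session". The Baseline Abstinence/Training Session paragraph repeats this ("they are asked to abstain from smoking for 24 hours prior to the session"). For the second test, starting right after V5, "participants will be asked to abstain from smoking for 24 hours prior to attending a final laboratory abstinence session". None of these names e-cigarettes, other tobacco or nicotine.

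**Check.** "Expired CO < 6 ppm or 50% reduction from baseline will be used to verify abstinence". For A2, "Procedures and measures will be identical to those used in the initial abstinence session".

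**Eligibility.** The Exclusion criteria remove people with "use of non-cigarette tobacco products or electronic cigarettes > 8 times in past 30 days", so 0 to 8 uses are allowed. They also remove people with "current use of nicotine replacement therapy (NRT) or other smoking cessation strategy".

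**Other text on tobacco.** In the Screening Session paragraph, the sentence on marijuana adds that participants "must avoid any additional tobacco such as cigarillos".

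**Other sources of information.** Table 1 marks timeline follow-back at V1 to V5 and urine for nicotine equivalents at V2 to V5, with neither at A1 or A2. Its footnote says urine is taken at all visits but analysed only for V4 and V5 of the VLNC arm. The end-of-day report on non-cigarette tobacco runs while study cigarettes are in use. The Risk/Benefit section gives the V1 follow-back a two-week look-back.

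**The concern.** Hypothesis 1b compares the arms on pain, pain interference and withdrawal at the 24-hour abstinence test, relative to the pre-intervention test. That comparison is meant to be made with nicotine withheld. The Background section itself says that nicotine has mild anti-nociceptive effects. A participant who vapes during the window has kept to the instruction as written and can pass the CO check, yet has taken the substance whose absence is being studied. Withdrawal and pain could then be understated.

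The plan treats other tobacco as important elsewhere: it is asked about weekly and in end-of-day reports, and disclosing it reduces the adherence bonus. The 24 hours in which nicotine intake bears most directly on the outcome are the ones with no matching question.

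**Working it through.** **1. Which sources cover each window?**

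| Source | A1 window | A2 window |
|---|---|---|
| Challenge instruction | smoking only | smoking only |
| Expired CO | yes, combustion only | yes, combustion only |
| Timeline follow-back | in part, through V1 | none after V5 |
| End-of-day report | no (starts with study cigarettes) | none stated after study cigarette use |
| Analysed urine | none | none (last is V5, VLNC only) |
| Medications check | yes, could show NRT | yes, could show NRT |

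That CO misses non-combusted nicotine is a general property of the marker, not a statement in the documents.

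On the A1 entry: A1 is day 0 and V1 is day 7 ± 2, so the A1 window opened 5 + 1 = 6 to 9 + 1 = 10 days before V1. A 14-day look-back contains it. A 7-day look-back, as the Weekly Sessions paragraph describes, would usually miss it. Recovery at A1 therefore rests on the two-week version being used and on its covering other products as well as cigarettes.

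**2. How often might an eligible participant use another product in 24 hours?** At the ceiling of 8 uses in 30 days, the rate is 8/30 = 0.267 per day.
- Poisson: 1 − exp(−0.267) = 23.4%.
- Eight uses placed at random on 30 days: 1 − (29/30)^8 = 23.8%.

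This is the heaviest eligible user at the usual rate. The sample average depends on how many such users enrol, which the documents do not give. If one in five were at the ceiling and the rest used nothing (assumed), the average would be 0.20 × 23.4% = 4.7%. At usual rates it cannot exceed the ceiling value. Behaviour while cigarettes are withheld may differ from usual.

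**3. The plan's power figure.** Sample size determination gives 70% to 96% for the group by abstinence-session interaction (N = 48, 2 occasions, d = 0.4 to 0.6, correlation 0.4, alpha 0.05). With f = d/2, λ = f²·N·m/(1 − ρ) and 1 and 46 degrees of freedom:
- d = 0.4: λ = 0.04 × 48 × 2 / 0.6 = 6.4, power 69.7%.
- d = 0.6: λ = 0.09 × 48 × 2 / 0.6 = 14.4, power 96.0%.

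The stated figures reproduce. No number in the plan is wrong on this point.

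**4. Illustration only.** Suppose a share p of participants, equal in both arms, were not nicotine-free and contributed no effect, so that d becomes d(1 − p). Power at correlation 0.4:

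| p (assumed) | d = 0.4 | d = 0.5 | d = 0.6 |
|---|---|---|---|
| 0 | 70% | 87% | 96% |
| 5% | 65% | 84% | 94% |
| 10% | 61% | 80% | 92% |
| 20% | 51% | 70% | 84% |

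This shows sensitivity to p. It is not an estimate of p.

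**The case against.** The case against has real content.

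- **Other tobacco is addressed.** Read plainly, the screening sentence ("must avoid any additional tobacco such as cigarillos") could cover smokeless and other tobacco throughout the study. This stands in part. The sentence sits with the marijuana rule and is not tied to the challenge. It does not name e-cigarettes, which the Exclusion criteria list separately from tobacco products. It also fits poorly with admitting users of up to 8 times in 30 days. The clearest gap is therefore e-cigarettes.
- **A1 is not blind.** A reader might infer that nothing would reveal use at either session. For A1 that is too strong, because the two-week follow-back at V1 reaches over the window. A1 also precedes randomisation, so use there is balanced in expectation and adds noise without favouring an arm.
- **Incentives.** A reader might infer that the adherence incentive has lapsed by A2. The documents do not support this outright: participants are told that two urine samples are picked at random, and the Table 1 footnote says urine is taken at all visits to keep up the impression of possible testing. They need not know that V5 is the last sample that counts.
- **NRT.** Current users are excluded and medications are reviewed at A1 and A2, so NRT is partly covered.
- **Missing pages.** Consent material is not in the available copy, so what participants are told there cannot be judged.

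None of this supplies a record of e-cigarette use in the A2 window.

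**Conclusion.** The point holds as a measurement gap, mainly for e-cigarettes and mainly at A2. As written, the plan lets a challenge count as verified although vaped nicotine was taken, and nothing scheduled would show it.

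A reader might go further and infer that NNC participants would substitute more, so that the Hypothesis 1b contrast shrinks by a calculable percentage. The documents do not support that. They give no prevalence of e-cigarette use and no rate of substitution under abstinence. VLNC participants may also take other nicotine: the plan cites 54–69% verified compliance in a prior study. Use mainly in NNC would shrink the contrast, and use mainly in VLNC would inflate it. Multiplying an assumed share of NNC users by an assumed loss gives the proportional shrinkage only if VLNC participants have no abstinence effect at A2, and the plan predicts a decrease in that arm, not its absence.

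The only size that follows from the plan's own limit is the roughly 23% chance for a participant at the eligibility ceiling, assuming usual-rate use spread at random. It is not a sample average. The change is worth making because it is cheap and protects a primary contrast.

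**What to change.** 1. Define A1 and A2, in the same words, as 24 hours' abstinence from all tobacco and nicotine products, including e-cigarettes. Reconcile the Screening Session sentence on additional tobacco, the two abstinence-session paragraphs and the Exclusion criteria.
2. At each of A1 and A2, add one recall item on the past 24 hours: any non-cigarette tobacco, e-cigarette or nicotine product, which one, and when last used.
3. Keep every session in the main analysis. Add a supportive analysis that sets aside sessions with reported use, by the same rule in both arms, and report the number of such sessions by arm.

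The cost is a change of wording, one item at two existing sessions, and one additional analysis. The stated power is unaffected, because the main analysis set does not change. The recall item is unverified, so it will miss undisclosed use, and some occasional e-cigarette users will be flagged as not abstinent.
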